Institution/Department : Kaohsiung Veterans General Hospital
Principal Investigator (PI) : [name]
Research Project Title : Efficacy of H2 receptor antagonist in prevention of
thienopyridine-related peptic ulcer
NCT Number : NCT02418312
Date of the document : 11 09 2018 (MM/DD/YYYY)

ABSTRACT

Background: Current U.S. guidelines recommended thienopyridine (e.g. clopidogrel) for patients who have major gastrointestinal intolerance or complications of aspirin. However, a recent study demonstrated that 12% of patients with a history of ulcer who took clopidogrel had ulcer bleeding within one year. Although proton pump inhibitor (PPI) can prevent recurrent peptic ulcer in clopidogrel users with a history of peptic ulcer, the interaction between PPIs and clopidogrel has drawn much attention recently. Several studies reported that certain PPIs could reduce clopidogrel's antiplatelet effects and increase cardiovascular events. Theses data suggested that PPIs may potentially inhibit the CYP2C19 pathway and interfere with the conversion of clopidogrel to active form. Therefore, searching for other gastroprotective agents to prevent gastrointestinal events for clopidogrel users is urgently needed in clinical practice.

Aims: To investigate the efficacy of histamine-2 receptor antagonist in the prevention of ulcer recurrence for thienopyridine users.

Methods: 228 thienopyridine (clopidogrel or ticlopidine) users with an ulcer history who do not have gastroduodenal ulcer at initial endoscopy are included. The patients will be randomly assigned to receive either (1) famotidine (40 mg before bedtime) or (2) placebo (before bedtime) for 6 months. Blood sampling for genotyping of *CYP2C19* is carried out on enrollment. Platelet aggregation tests are performed in Day 1 and Day 28. Follow-up endoscopy is carried out at the end of the 6th month and whenever severe epigastric pain, hematemesis or melena occurs. Additionally, the episodes of acute coronary syndrome and cerebral vascular accident will be carefully evaluated during the treatment period. Finally, the ulcer recurrence rate, ulcer bleeding rate, incidence of acute

coronary syndrome and cerebral vascular accident between the treatment groups will be compared by chi-square test. Additionally, the independent factors predicting ulcer recurrence will be investigated by multivariate analysis. Furthermore, the effect of *CYP2C19* genetic polymorphism on the development of cardiovascular events and platelet aggregation will be analyzed.

INTRODUCTION

Platelet activation and aggregation play an important role in the pathogenesis of arterial thrombosis and lead to ischemic events. Thienopyridine (clopidogrel or ticlopidine) inhibits platelet function by selectively and irreversibly blocking the adenosine diphosphate (ADP) receptor on platelets, thereby affecting ADP-dependent activation of the GpIIb-IIIa complex, the major receptors for fibrinogen present on the platelet surface.^{1, 2} Alone or in association with aspirin, clopidogrel is a thienopyridine, which has successfully proved to be beneficial in the treatment of acute coronary syndrome³ and prevention of ischemic events in patients with atherosclerotic diseases.^{4,5}

The CAPRIE study showed that long-term administration of clopidogrel to patients with atherosclerotic vascular disease is more effective than aspirin in reducing the combined risk of ischemic events.⁶ Additionally, Clopidogrel induced fewer episodes of gastrointestinal bleeding than aspirin.^{6,7} The American College of Cardiology-American Heart Association guidelines therefore recommend clopidogrel as an alternative to aspirin for patients with unstable angina or non-ST-segment elevation myocardial infarction who have an aspirin intolerance.⁸

However, a recent study demonstrated that 12% of patients with a history of ulcer who took clopidogrel had ulcer bleeding within one year.⁹ Furthermore, the cumulative incidence of recurrent bleeding in clopidogrel users who had ulcer bleeding history (subjects with high gastrointestinal risk) was higher than that in patients who took aspirin plus proton pump inhibitor (PPI).¹⁰ The mechanisms leading to recurrent ulcer bleeding among patients receiving

clopidogrel are unclear. Nonetheless, an animal study revealed that platelet ADP-receptor antagonists impair the healing of gastric ulcers by suppressing the release of platelet-derived growth factors.¹¹ We therefore speculate that clopidogrel may also hinder ulcer healing and/or precipitate ulcer formation in humans.

Recently, we have proved that proton pump inhibitor can effectively prevent recurrent

peptic ulcers among atherosclerotic patients with a history of peptic ulcer.¹² However, the interaction of PPIs and clopidogrel has raised the concern for the safety of combination use of the two medicines.¹³⁻¹⁵ Clopidogrel is a prodrug, which must be absorbed in the gastrointestinal tract, and metabolized in the liver to generate active metabolites and acquires its anti-platelet properties. The metabolism of clopidogrel involves CYP2C19 isoenzyme, which is also the key enzyme for the metabolism of most PPIs.¹⁶ This has led to the assumption that some PPIs may potentially inhibit the CYP2C19 pathway and interfere with the conversion of clopidogrel to active form. Three large retrospective observation studies also reported that patients prescribed clopidogrel who also took PPIs had significant increases in cardiovascular events.¹⁷⁻

¹⁹

Famotidine is a histamine H₂-receptor antagonist that has proved to be well tolerated and able to prevent and heal peptic ulcers in patients receiving conventional NSAIDs.²⁰⁻²² The FAMOUS (Famotidine for the Prevention of Ulcers in Users of Low-dose Aspirin) trial documented that famotidine is effective in the prevention of peptic ulcers and erosive esophagitis in patients taking low-dose aspirin.²³ However, famotidine is inferior to pantoprazole in preventing recurrence of aspirin-related peptic ulcers or erosions in patients with aspirin-related peptic ulcers/erosions.²⁴ The current study is designed to assess the efficacy of histamine-2 receptor antagonist in the prevention of ulcer recurrence for thienopyridine users.

References

1. Savi P, Nurden P, Nurden AP, Levy-Toledano S, Herbert JM. Clopidogrel: a review of

- its mechanism of action. *Platelets* 1998;9:251-255.
2. Boeynaems JM, van Giezen H, Savi P, Herbert JM. P2Y receptor antagonist in thrombosis. *Curr Opin Investig Drugs* 2005;6:257-282.

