We will screen for eligible patients who have a past history of gastroduodenal ulcer and underwent endoscopy for dyspeptic symptoms or routine screening, while receiving thienopyridine (either clopidogrel or ticlopidine) therapy to prevent ischemic events. We enroll patients in the study if they meet the following criteria: endoscopic examination reveals normal appearance or pictures of gastritis only; they have received thienopyridine for at least two weeks; they have an atherosclerotic disease such as ischemic heart disease or stroke; they require long-term anti-platelet therapy; and they are adult patients aged ≥ 20 years. Patients are excluded if they have a history of gastric or duodenal surgery other than oversewing of a perforation; if they are allergic to the study drugs; if they require long-term treatment with non-steroidal anti-inflammatory drugs (NSAIDs), corticosteroids, aspirin, or anticoagulant agents; if they are pregnant; if they have active cancer, acute serious medical illness or terminal illness; and if they have gastroesophageal reflux disease.

Study Protocol

Randomization and treatment

Eligible 228 patients are randomly assigned to receive either (1) 40 mg of famotidine (40 mg before bedtime) or (2) placebo (before bedtime) for 6 months. Randomization was carried out with the use of a computer-generated list of random numbers. An independent staff member assigned the treatments according to consecutive numbers that were kept in sealed envelopes. Anticoagulants, cyclooxygenase-2 inhibitors, conventional NSAIDs, aspirin, over-the-counter analgesics, corticosteroids, misoprostol, PPIs, sucralfate are prohibited. The administration of an antacid (Iwell, Everest, Taiwan) was permitted for the control of dyspeptic symptoms. Compliance with the regimen are assessed by counting the pills that are returned. If *Helicobacter pylori* (*H pylori*) infection is documented on recruitment, a seven-day course of anti-*H pylori* therapy is administered.²⁵ Urea breath test²⁶ is performed at four weeks after the end of anti-*H pylori* therapy. Patients in whom *H pylori* infection is not eradicated, as indicated by positive results of urea breath

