tests, receive a ten-day course of quadruple therapy consisting of esomeprazole 40 mg b.d., bismuth subcitrate 120 mg q.d.s., tetracycline 500 mg q.d.s., metronidazole 250 mg q.d.s. An additional ^{13}C urea breath test was conducted to assess the final *H pylori* status two weeks following the six-month trial for all the patients who have *H pylori* infection on recruitment. Eradication is defined as a negative result of the final urea breath test.

Blood sampling for genotyping of *CYP2C19* is carried out on enrollment. Platelet aggregation tests are performed in Day 1 and Day 28. The *CYP2C19* genotype is determined using the polymerase chain reaction-restriction fragment length polymorphism (PCR-RFLP) as previous description.^{27,28} Genotypes are classified into three groups: homogeneous extensive metabolizer (homEM; *CYP2C19**1/*CYP2C19**1); heterogeneous extensive metabolizer (hetEM; *CYP2C19**1/*CYP2C19**2 and *CYP2C19**1/*CYP2C19**3); poor metabolizer (PM; *CYP2C19**2/*CYP2C19**2, *CYP2C19**2/*CYP2C19**3, and *CYP2C19**3/*CYP2C19**3).

Detection of H pylori on recruitment

On initial endoscopy, a biopsy specimen was obtained from the greater curvature within 5 cm of the pylorus for rapid urease test. A negative CLO test was defined by the absence of a change in color after 24 hours. Additionally, one specimen taken from the greater curvature within 5 cm from the pylorus and another taken from the greater curvature of middle body were subjected to microscopic examination for *H pylori* with the use of hematoxylin and eosin stain and Warthin-Starry stain if necessary. *H pylori* was considered to be present if either one of the two tests was positive; it was considered to be absent when both tests were negative.

Follow-up

Patients are followed up as outpatients with visits every month. Upper gastrointestinal and cardiovascular symptoms are assessed at each visit. They are asked to return to the outpatient clinic if they have persistent dyspeptic symptoms (epigastric pain, fullness, nausea or vomiting) and to report to the emergency room if they have evidences of gastrointestinal bleeding (hematemesis, melena, or sudden onset of severe epigastric pain), cardiovascular events (chest pain, syncope, or

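### Does the multivariate analysis of ulcer recurrence need a stated model, factor list and selection rule?

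*Combined protocol and SAP*

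**What the plan says.** The analysis is described only in the Abstract, under Methods. Ulcer recurrence, ulcer bleeding and the vascular outcomes "between the treatment groups will be compared by chi-square test". The next sentence adds that "the independent factors predicting ulcer recurrence will be investigated by multivariate analysis". A third sentence plans to study CYP2C19 genotype, but against cardiovascular events and platelet aggregation, not ulcers.

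The Patients and Methods section covers population, randomisation, H pylori, genotyping, follow-up and end points. It does not mention the multivariate analysis again. The model type, the candidate factors, the place of treatment arm and any selection rule are therefore unstated.

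The document mentions several variables that could be candidates:

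- In Study population: the type of thienopyridine ("receiving thienopyridine (either clopidogrel or ticlopidine) therapy to prevent ischemic events"), the reason for endoscopy ("underwent endoscopy for dyspeptic symptoms or routine screening"), the endoscopic finding ("endoscopic examination reveals normal appearance or pictures of gastritis only"), the underlying vascular disease, and age.
- In Randomization and treatment and Detection of H pylori: infection at recruitment, genotype in three groups, and platelet aggregation ("Platelet aggregation tests are performed in Day 1 and Day 28").
- After randomisation: pill counts ("Compliance with the regimen are assessed by counting the pills that are returned"), the second aggregation test, and a final breath test done "two weeks following the six-month trial for all the patients who have" H pylori at entry.

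**The concern.** A search for independent predictors with an open list of factors and few events is a familiar source of unreliable findings. Chance can produce a significant factor, and a real factor reported only because it passed a threshold will tend to be overstated. If variables that arise after randomisation entered the model, they could reflect treatment or behaviour during the trial rather than baseline risk. The final breath test is taken after the month-6 endoscopy that decides the end point.

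This is also the only adjusted analysis of the primary outcome that the plan mentions. If the arms differed by chance on something important, readers might look to it for an adjusted treatment effect, and the choice of adjustment would then be made after the data were seen. At stake are the credibility of any factor labelled independent and, less directly, the treatment comparison.

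**Working it through.** **Inputs.** From the documents: 228 patients, a 6-month endoscopic ulcer end point, and missing follow-up endoscopy counted as normal. Assumed: 1:1 allocation (114 per arm) and the ulcer rates, because the plan gives none. The only rate in the document is 12% ulcer bleeding within one year, which is a different outcome. Converted to six months it is 1 − (1 − 0.12)^0.5 = 6.2%, or about 14 events if it applied to all 228. Endoscopic ulcers should be more frequent than bleeds. The plan has no event count or model size to reproduce.

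**Events per coefficient.** Expected ulcers = 114 × (placebo rate + famotidine rate). Ten coefficients are treatment plus eight factors, with genotype taking two.

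| Assumed rates | Expected ulcers | Per coefficient (÷ 10) |
|---|---|---|
| 20% vs 8% | 114 × 0.28 = 31.9 | 3.2 |
| 15% vs 5% | 114 × 0.20 = 22.8 | 2.3 |
| 12% vs 3% | 114 × 0.15 = 17.1 | 1.7 |

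A ten-coefficient model would be thin. That part of the concern is right under these rates.

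**False predictors.** Trials were simulated (20,000 per setting) with all eight factors null and independent. Assumed distributions: H pylori 40%; genotype 40/46/14%; ticlopidine 15%; gastritis 50%; dyspepsia 50%; ischemic heart disease 60%; age and Day 1 aggregation standard normal. The table gives the share of trials with at least one factor at p < 0.05.

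| Procedure | 20% vs 8% | 15% vs 5% | 12% vs 3% |
|---|---|---|---|
| All eight factors in one model | 32.5% | 31.2% | 29.9% |
| Screen at p < 0.10, then model | 29.3% | 28.0% | 26.2% |
| Treatment plus two factors | 7.6% | 7.2% | 6.8% |

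The nominal rate for k independent tests is 1 − 0.95^k, which is 33.7% for k = 8 and 9.8% for k = 2. Three things follow.

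1. The first row is a fixed model. A plan that named all eight factors and that model in advance would have the same 30–32%. The figure measures how many factors are tested, not the lack of a list.
2. The fall to about 7% comes from testing two factors instead of eight. Naming them contributes nothing to it.
3. The rate falls slightly as ulcers become fewer, and falls again with screening. Sparse events and selection do not drive the false positives here.

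**How many candidates there are.** Eight is generous. Age, endoscopic finding, reason for endoscopy and vascular disease appear only as screening or eligibility wording, and the document has no baseline data list. Genotype and platelet aggregation are linked to other outcomes. Without genotype and aggregation, six factors remain and simulation gives 22–24% (nominal 1 − 0.95^6 = 26.5%). Without the four eligibility items as well, two remain: H pylori and thienopyridine type.

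**Overstated odds ratios.** With one true factor at 40% prevalence, reported only if it survives screening, a true odds ratio of 2 is found in 25–42% of trials with a median estimate of 2.8–3.8. A true odds ratio of 3 is found in 53–79%, median 3.4–4.4. When always reported from a two-factor model, the medians are 2.0 and 3.1. The inflation is real, but it comes from reporting only what passes. The simulated screen is itself a fixed rule, so writing that rule into the plan would leave the inflation unchanged. The plan does not say that only selected factors will be reported.

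**Treatment comparison.** With no treatment effect (20% or 12% in both arms), the chi-square rejects in 4.8% and 5.0% of trials. Taking the smallest treatment p-value over the chi-square, eight one-factor models, the full model and the screened model gives 6.4%.

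**The case for a change.** The strongest case for a change is that this is the combined protocol and SAP, it promises to identify independent factors for its own primary outcome, and it says nothing about how. Specifying a model with treatment and two named baseline factors would need no new data and would leave the primary test and sample size as they are. It would also rule out variables arising after randomisation. An open choice of model could push the false-positive rate above that of any fixed model, and the figures for the factors do not measure this.

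The omission stands, and so does the warning that a long factor list would be supported by few ulcers. The rest is weaker. A limit of two factors is not derived from the plan: a placebo rate of 12–25% with a risk ratio of 0.25–0.5 gives about 17–43 ulcers, which supports roughly 2–4 coefficients at ten events each or 3–8 at five. Such a limit would also largely replace a search for predictors with an adjusted treatment model, which is a change of aim and not only of wording.

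The entry of variables arising after randomisation is conjecture. The final breath test is done only in patients infected at entry, so it is undefined for the others. It also confirms the result of therapy given during the trial, so the date of the test is not the date of the state it measures. An analyst should still keep it out of a baseline risk model, and nothing in the plan suggests otherwise.

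**Conclusion.** No change to the plan follows. The multivariate analysis is described in one sentence without model, factors or selection rule, but this is missing detail in a secondary, hypothesis-generating analysis, and it is not an error. A competent analyst would use logistic regression with arm and a modest set of baseline factors, report all the estimates with intervals, and present the result as exploratory. The sentence in the Abstract permits all of this.

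The risk of about 30% for a false predictor belongs to testing eight factors, named or not, and is lower for the shorter lists that the document supports more firmly. Overstated odds ratios would arise only if non-significant factors went unreported. The comparison of famotidine with placebo has its own valid test, and even deliberate picking among adjusted models would move its type I error only from about 5% to 6.4%.

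These sizes rest on assumed ulcer rates, 1:1 allocation, and assumed independent factors. With all binary factors set to 30% or 50% prevalence, the false-predictor rate for eight factors stays between 24% and 33%. The reading of that rate as multiplicity does not depend on the assumed ulcer rates.

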We will screen for eligible patients who have a past history of gastroduodenal ulcer and underwent endoscopy for dyspeptic symptoms or routine screening, while receiving thienopyridine (either clopidogrel or ticlopidine) therapy to prevent ischemic events. We enroll patients in the study if they meet the following criteria: endoscopic examination reveals normal appearance or pictures of gastritis only; they have received thienopyridine for at least two weeks; they have an atherosclerotic disease such as ischemic heart disease or stroke; they require long-term anti-platelet therapy; and they are adult patients aged ≥ 20 years. Patients are excluded if they have a history of gastric or duodenal surgery other than oversewing of a perforation; if they are allergic to the study drugs; if they require long-term treatment with non-steroidal anti-inflammatory drugs (NSAIDs), corticosteroids, aspirin, or anticoagulant agents; if they are pregnant; if they have active cancer, acute serious medical illness or terminal illness; and if they have gastroesophageal reflux disease.

Study Protocol

Randomization and treatment

Eligible 228 patients are randomly assigned to receive either (1) 40 mg of famotidine (40 mg before bedtime) or (2) placebo (before bedtime) for 6 months. Randomization was carried out with the use of a computer-generated list of random numbers. An independent staff member assigned the treatments according to consecutive numbers that were kept in sealed envelopes. Anticoagulants, cyclooxygenase-2 inhibitors, conventional NSAIDs, aspirin, over-the-counter analgesics, corticosteroids, misoprostol, PPIs, sucralfate are prohibited. The administration of an antacid (Iwell, Everest, Taiwan) was permitted for the control of dyspeptic symptoms. Compliance with the regimen are assessed by counting the pills that are returned. If *Helicobacter pylori* (*H pylori*) infection is documented on recruitment, a seven-day course of anti-*H pylori* therapy is administered.²⁵ Urea breath test²⁶ is performed at four weeks after the end of anti-*H pylori* therapy. Patients in whom *H pylori* infection is not eradicated, as indicated by positive results of urea breath

tests, receive a ten-day course of quadruple therapy consisting of esomeprazole 40 mg b.d., bismuth subcitrate 120 mg q.d.s., tetracycline 500 mg q.d.s., metronidazole 250 mg q.d.s. An additional ^{13}C urea breath test was conducted to assess the final *H pylori* status two weeks following the six-month trial for all the patients who have *H pylori* infection on recruitment. Eradication is defined as a negative result of the final urea breath test.

Blood sampling for genotyping of *CYP2C19* is carried out on enrollment. Platelet aggregation tests are performed in Day 1 and Day 28. The *CYP2C19* genotype is determined using the polymerase chain reaction-restriction fragment length polymorphism (PCR-RFLP) as previous description.^{27,28} Genotypes are classified into three groups: homogeneous extensive metabolizer (homEM; *CYP2C19**1/*CYP2C19**1); heterogeneous extensive metabolizer (hetEM; *CYP2C19**1/*CYP2C19**2 and *CYP2C19**1/*CYP2C19**3); poor metabolizer (PM; *CYP2C19**2/*CYP2C19**2, *CYP2C19**2/*CYP2C19**3, and *CYP2C19**3/*CYP2C19**3).

Detection of H pylori on recruitment

On initial endoscopy, a biopsy specimen was obtained from the greater curvature within 5 cm of the pylorus for rapid urease test. A negative CLO test was defined by the absence of a change in color after 24 hours. Additionally, one specimen taken from the greater curvature within 5 cm from the pylorus and another taken from the greater curvature of middle body were subjected to microscopic examination for *H pylori* with the use of hematoxylin and eosin stain and Warthin-Starry stain if necessary. *H pylori* was considered to be present if either one of the two tests was positive; it was considered to be absent when both tests were negative.

Follow-up

Patients are followed up as outpatients with visits every month. Upper gastrointestinal and cardiovascular symptoms are assessed at each visit. They are asked to return to the outpatient clinic if they have persistent dyspeptic symptoms (epigastric pain, fullness, nausea or vomiting) and to report to the emergency room if they have evidences of gastrointestinal bleeding (hematemesis, melena, or sudden onset of severe epigastric pain), cardiovascular events (chest pain, syncope, or

sudden onset of severe palpitation) or cerebrovascular accidents (conscious disturbance, hemiparesis, or dysphagia). Follow-up endoscopy with biopsy for urease test is performed whenever persistent dyspepsia, severe epigastric pain, hematemesis or melena occurred and at the end of the 6th month. The endoscopists who performed follow-up endoscopy are unaware of the treatment group assignments. The events of acute coronary syndrome and cerebral vascular accidents during the study period are carefully monitored and assessed.

End points

The primary end point are the occurrence of gastric and/or duodenal ulcers, as determined by endoscopy, during the 6-month study period. An ulcer is defined as a circumscribed mucosal break at least 0.5 cm in diameter (measured using endoscopy forceps) and with a perceptible depth.^{10,12} Only events that are confirmed by the adjudication committee and that occurred during treatment are included in the analysis. Patients who do not have follow-up endoscopic examination are assumed to have had normal findings. The secondary endpoints are: (1) the occurrence of ulcer or erosion bleeding as defined according to pre-specified criteria – namely, hematemesis or melena documented by the admitting physician, with ulcers or bleeding erosions confirmed on endoscopy, or a decrease in the hemoglobin level of at least 2 g deciliter in the presence of endoscopically documented ulcers or erosions.¹⁰ An erosion is defined as a flat mucosal break of any size;¹⁰ (2) the occurrence of unstable angina defined as rest angina (angina occurring at rest and prolonged more than 20 minutes), new-onset angina (of at least the Canadian Cardiovascular Society Class III severity) and increasing angina (angina occurring more frequently, longer in duration) with ischemic changes in electrocardiogram;²⁹ (3) acute myocardial infarction defined as at least two positive results of typical chest pain, evolutionary electrocardiogram changes and evolutionary cardiac enzyme changes; (4) the occurrence of ischemic stroke defined as sudden onset of neurological deficit due to cerebral ischemia documented by computed tomography; (5) vascular death defined as death due to cardiovascular diseases or cerebrovascular accidents. Only events that are confirmed by the cardiovascular events review board are included in the analysis.

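### An ulcer complication that never reaches endoscopy meets no end point, and the patient is scored as ulcer-free

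*Combined protocol and SAP*

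**What the plan says.** All the relevant rules are in Patients and Methods, End points, of the combined protocol and SAP.

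- Primary end point: "The primary end point are the occurrence of gastric and/or duodenal ulcers, as determined by endoscopy, during the 6-month study period".
- What counts as an ulcer: "An ulcer is defined as a circumscribed mucosal break at least 0.5 cm in diameter (measured using endoscopy forceps) and with a perceptible depth".
- Patients not examined: "Patients who do not have follow-up endoscopic examination are assumed to have had normal findings". No exception is made for patients who died, had surgery or had clinical evidence of an ulcer complication.
- Which events enter: "Only events that are confirmed by the adjudication committee and that occurred during treatment are included in the analysis".
- Bleeding, first route: "hematemesis or melena documented by the admitting physician, with ulcers or bleeding erosions confirmed on endoscopy". The second route is a hemoglobin fall of at least 2 g per deciliter, and it too requires ulcers or erosions documented at endoscopy.
- Death: "vascular death defined as death due to cardiovascular diseases or cerebrovascular accidents". No other death end point is listed.

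Perforation is named in no end point. The word occurs only in Study population, where patients are excluded for a "history of gastric or duodenal surgery other than oversewing of a perforation".

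The Follow-up section limits the gap. It calls for endoscopy when persistent dyspepsia, severe epigastric pain, hematemesis or melena occurs, as well as at month 6.

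**The concern.** In most trials with an endoscopic end point, the awkward patient is one whose ulcer status is unknown because a scheduled examination was missed. This is a different patient. The complication is known and documented in the hospital record, but not by endoscope, and the written rules override that knowledge. The patient stays in the denominator with a normal result.

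The events concerned are the most severe form of what famotidine is meant to prevent. A trial of ulcer prevention that codes a proven, possibly fatal, ulcer complication as a success is hard to defend, even if it happens once. A sensitivity analysis for missed endoscopies would not repair this. It would leave the bleeding definition as it is and would add no count of gastrointestinal or all-cause deaths.

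**Working it through.** **Step 1: trace patients through the end points.** The plan gives no figure of its own on this point, so the check starts with the definitions.

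| Patient, during treatment | Primary (ulcer) | Bleeding | Vascular death |
|---|---|---|---|
| Perforated ulcer proven at surgery, imaging or autopsy; no endoscopy | No: not determined by endoscopy, so assumed normal | No: no endoscopic lesion | No, even if fatal: the cause is gastrointestinal |
| Massive hematemesis, death before endoscopy | No: assumed normal | No: both routes need an endoscopic lesion | No: the cause is gastrointestinal |
| Ulcer complication that reaches the symptom-triggered endoscopy, ulcer of at least 0.5 cm, confirmed by the committee | Yes | Yes, if the bleeding criteria are met | Not relevant |

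The remaining secondary end points (unstable angina, myocardial infarction, ischemic stroke) do not apply. The first two patients therefore contribute no event anywhere. The third shows where the gap ends: it covers only complications that bypass endoscopy.

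**Step 2: how many patients.** Inputs:
- 12% ulcer bleeding within one year in clopidogrel users with an ulcer history (Abstract and Introduction; background, not a design input).
- 228 patients in total (Study Protocol). The allocation ratio is not stated; 114 per arm is assumed.
- Fraction of bleeds that never reach endoscopy: not in the documents. Assumed 5-15%, with 2-20% as a wider range.

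Six-month risk at a constant hazard: 1 - (1 - 0.12)^0.5 = 0.0619. Simple halving gives 0.06.

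Placebo bleeds: 114 × 0.0619 = 7.1 (or 114 × 0.06 = 6.8), so about 7.

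Missed in the placebo arm: 0.05 × 7 = 0.35 to 0.15 × 7 = 1.05, so about 0 to 1.

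Wider bound for the whole trial, giving both arms the 12% rate: 228 × 0.0619 = 14.1. Then 0.02 × 14.1 = 0.3 and 0.20 × 14.1 = 2.8.

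Perforations would add to these counts, but the documents give no rate for them.

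**Step 3: what one patient does.** With 114 per arm, each miscoded patient moves the risk difference by 1/114 = 0.88 percentage points.

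**Step 4: direction.** Let the true risks be p_P (placebo) and p_F (famotidine), and let a share s of true events be counted in each arm, with no false events. The observed risk ratio is (s × p_F)/(s × p_P) = p_F/p_P, which is unchanged. The observed risk difference is s × (p_P - p_F), which is slightly smaller. If the share differs by arm, losses in placebo understate the benefit and losses in famotidine overstate it. Nothing in the documents fixes which occurs.

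**The case against.** The strongest reply is that the plan already sends these patients to endoscopy. The Follow-up section tells patients with hematemesis, melena or sudden severe epigastric pain to go to the emergency room, and requires endoscopy for such symptoms. Most complications will be seen that way and will count, even if the patient later dies. This stands, and it is why the point is confined to patients who die first or go directly to surgery. A reader might infer that no perforation or ulcer death could ever be counted; the text does not support that.

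Endoscopic confirmation is also an objective standard, referenced in End points to earlier studies. That too stands, and is a reason to keep the endoscopy-only result alongside a wider one.

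The adjudication committee might in practice accept surgical or autopsy evidence. As written, however, its role is to restrict which events enter, and nothing allows it to accept evidence other than endoscopy.

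Deaths may be reported as safety data elsewhere. The supplied text ends at End points, and its reference list stops at 22 although citations run to 29, so its silence on safety reporting is weak evidence. It would be wrong to conclude that deaths go unreported. What can be said is that no listed end point counts them, and that the comparisons named in the Abstract include neither perforation nor death.

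The 12% figure may not transfer. This trial enrols patients with a normal or gastritis-only endoscopy and treats *H pylori* infection, so 7 bleeds may be too many. The exception for an oversewn perforation shows only that some candidates may have perforated before; it gives no on-study rate.

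**Conclusion.** The gap is real on the text and small in expected number. A complication that never reaches endoscopy meets no end point, and the assumed-normal rule turns it into an ulcer-free result. About 0 to 1 placebo patient would be affected, or 0.3 to 2.8 in the whole trial on the wider range. These counts rest on an assumed missed fraction, assumed equal allocation, a constant hazard and a background bleeding rate that may be too high for this population. They leave out perforations.

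Two stronger conclusions are tempting. One is that the results are biased towards no effect. That would require the lost events to fall mainly on placebo and to be lost in unequal proportion if the risk ratio is to move; the documents establish neither. The other is that significance would be gained or lost. With so few patients, that depends on the counts and the test chosen for illustration, and the documents give no expected ulcer rates to anchor them.

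The case for change rests on the severity of the events and on coding a documented failure as a success.

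**What to change.** Amend End points as follows.

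1. Count as a primary event any gastric or duodenal ulcer or perforation documented by endoscopy, surgery, imaging or autopsy during treatment and confirmed by the adjudication committee, with its members blinded to arm. State that the assumed-normal rule does not apply to these patients. Blinding needs to be written in, because the plan states it only for the follow-up endoscopists.
2. Keep the endoscopy-confirmed bleeding definition as the main secondary end point. Add a sensitivity analysis that includes probable upper gastrointestinal bleeding without endoscopy, adjudicated blind to arm.
3. Report all-cause death by arm, with deaths from gastrointestinal bleeding or perforation shown separately, beside vascular death.
4. Report the primary result on the endoscopy-only definition as well.

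The cost is low: amended wording, a line on the adjudication form, and use of the existing committee and hospital records. Patient care does not change. Item 1 is still a substantive change to the primary definition, which would depart slightly from the earlier studies cited for it, and a few events will lack endoscopic proof. Item 4 lets a reader see the effect of both.
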